11 DATA MANAGEMENT AND STATISTICS

11.1 SAMPLE SIZE/POWER CONSIDERATIONS

No sample size and power calculations have been conducted for this study as pharmacokinetic evaluations for two hundred (200) eligible subjects has been requested.

11.2 INTERIM ANALYSIS

An interim analysis of bismuth concentrations and study safety parameters is planned eighteen (18) months following the market launch of Pylera® in France, when 75 to 100 evaluable patients are expected to have been included in the study.

The analysis will be conducted to present the summary of the derived population PK parameters and the Confidence Interval. If low variability is found, the sponsor and the study project team will stop the study at 100 subjects, after consultation with Regulatory Agency.

11.3 SOURCE DOCUMENTS

All individual entries in source documentation require signature and date by the authors. All typed or dictated documents and computer printouts must be signed and dated by the Investigator to confirm review.

Preliminary laboratory reports including faxed copies must be initialed and dated and need to be retained. Final laboratory reports should be initialed and dated by the Investigator to confirm review. Original laboratory reports should be kept in file.

The following are considered to be source data:

- Medical charts, clinic charts, nurses' notes, medical correspondence regarding the human subject
- Subject progress notes
- Pathology reports
- Laboratory reports
- Study worksheets

Electronic (paperless) hospital reporting systems – the Investigator must sign and date a hard copy of this data for this to be considered a source document.

11.4 DATA COLLECTION AND CASE REPORT FORM MONITORING

All data will be collected using a paper-based multi-part Case Report Form (CRF).

The progress of the study will be monitored by telephone communication between site personnel and an Aptalis Pharma US, Inc designee. On-site visits will be performed at the end of the study to ensure compliance with the study protocol and to perform review of the subject CRF against the source document (subjects' medical record). On-site visits will also ensure that adequate records of clinical study supplies are maintained and to assess the continued suitability of the site.

11.5 DATA MANAGEMENT

A Data Management Plan and Data Review Plan will be developed to ensure the quality of the data.

11.5.1 Data Capture

Simplified data collection to characterize subject profile will be conducted using a paper-based multi-part CRF, which will capture:

- socio-demographic data, including age, sex, height, weight
- screening/baseline parameters prior to prescription of Pylera®, including medical history, vital signs, and results of a diagnostic *H. pylori* test (breath test, biopsy, or other test at the discretion of the Investigator) (if available), prescribed treatments, including:
 - Pylera® (indication, dose and duration of treatment)
 - PPI (indication, dose and duration of treatment)
 - other concomitant treatment(s)
- prior and concomitant medications
- AEs
- CNS AEs

A specific form will be completed by the subject and/or sampling laboratory to capture data related to PK blood draw. This form will capture subject characteristics, time of drug ingestion, time of sample, time elapsed since first drug intake, and time elapsed since last drug intake. This specific form will be completed at each blood draw and will be sent with each sample.

A specific form entitled “Targeted follow-up form – Pylera® eradication therapy failure” will be used to document subjects who demonstrate a positive diagnostic *H. pylori* test (breath test, biopsy, or other test at the discretion of the Investigator) infection at the EOS Visit. This form will permit a systematic assessment of the post-marketing case reports of lack of efficacy.

11.6 PROTOCOL DEVIATIONS

A protocol deviation is an unanticipated or unintentional divergence or departure from the expected conduct of the approved study that is not consistent with the current clinical protocol,

consent document or study addenda that could affect efficacy or safety parameters. Examples of protocol deviations include, but are not limited to, the following deviations:

- Enrolment of subjects outside protocol inclusion/exclusion criteria
- Changes in procedures initiated to eliminate immediate hazards to study subjects that could affect safety parameters
- Use of prohibited medication that could affect safety parameters
- Medically relevant omission of procedures
- Medically relevant sample loss
- Medication/intervention errors (e.g. incorrect study medication/intervention, incorrect dosage of the study medication)
- Significant change in the visit window or unapproved procedural deviation that could affect safety parameters
- Lack of subject adherence to study procedures
- Breach of confidentiality or privacy whereby confidential information about a subject is revealed in inappropriate settings, or to persons without a need to know, or by data exposure (computer security breach, documents left unsecured)
- Significant deviation from the consenting process (e.g. person who signed was not qualified, consent form was not signed)

All major protocol deviations must be reported on the Protocol Deviation Report Form provided and should be sent to the REB/IEC/IRB as per local policies.

In the case of a major protocol deviation, the Investigator will prospectively consult for appraisal, will fill out the appropriate section of the Protocol Deviation Report Form and will provide any supporting medical rationale/assessments. The sponsor will promptly evaluate all Protocol Deviation Report Forms and will document decision on subject management and follow-up instructions (if applicable) in the appropriate section of the form. A copy of the signed and dated form will be sent to the Investigator. Any major protocol deviation must obtain approval from the sponsor and from the Institution's IRB for the subject to enter or to remain in the trial.

In the event that an unreported major protocol deviation is discovered by the Investigator, the Protocol Deviation Report Form must be filled out immediately and sent to the sponsor for a retrospective appraisal.

In the case of minor protocol deviations, the Investigator should verify which ones need to be submitted to the REB/IEC/IRB as per local policies. Minor protocol deviations are not reported on the Protocol Deviation Report Form and will be reported on a comment page of the questionnaire.

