1.2 RATIONALE FOR THE STUDY

As part of the Pylera® MAA, a post-marketing PK program to be conducted in France was requested to observe potential changes in bismuth concentrations arising from real-life use of Pylera® in the general population, including poor compliance, misuse, or the concomitant use of other medications.

The present study is designed to address this request.

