4.6 DISCONTINUATION CRITERIA

A subject has the right to withdraw from the study at any time for any reason without penalty or prejudice. The Investigator also has the right to withdraw a subject from the study if he/she feels it is in the best interest of the subject or if the subject is uncooperative or noncompliant. Should a subject decide to withdraw, all efforts will be made to complete and report the observations and early withdrawal procedures as thoroughly as possible.

Subjects who withdraw subsequent to the signing consent but before receiving the prescription for Pylera® will be considered “screening failures” and will be replaced to ensure that 200 evaluable subjects complete the study.

Discontinuation may occur because of any one of the following reasons among others:

#	Discontinuation criteria
1	The subject has been included in violation of the inclusion / exclusion criteria

2	The subject chooses to discontinue participation for personal reasons (moving away, no time, etc.)
3	The subject chooses to discontinue, or is discontinued by the Investigator or the sponsor, due to an AE
4	The Investigator or the sponsor discontinues the subject for a significant protocol deviation
5	A newly developed illness, as determined by the physician in charge, that compromises continued participation
6	The subject uses a prohibited medication during the study (as described under Section 4.3.2)
7	In the Investigator or sponsor's judgment, withdrawal from the study would be in the subject's best interest (e.g., an immediate medical or surgical procedure is required that would compromise the subject's continued participation, lack of adequate therapeutic response resulting in intolerable symptoms or unacceptable risk)
8	The subject is uncooperative or does not comply with the protocol requirements (e.g., failure to return for scheduled visits at the enrolling study site, failure to complete study evaluation, etc.)
9	The sponsor terminates the study

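### Sections 4.6 and 11.6 allow subjects to be removed for the dosing departures that Section 1.2 wants observed, and no post-treatment bismuth sample is listed for those who leave or stop early

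*Protocol*

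**What the plan says.** All references are to the protocol.

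- **Purpose.** Section 1.2 says the post-marketing programme was requested to observe changes in bismuth "arising from real-life use of Pylera® in the general population, including poor compliance, misuse, or the concomitant use of other medications".
- **Withdrawal.** Section 4.6 gives the investigator the right to withdraw a subject "if he/she feels it is in the best interest of the subject or if the subject is uncooperative or noncompliant". Criterion 4 in the same section reads "The Investigator or the sponsor discontinues the subject for a significant protocol deviation".
- **Deviations.** Section 11.6 includes among its examples "Medication/intervention errors (e.g. incorrect study medication/intervention, incorrect dosage of the study medication". Any major deviation "must obtain approval from the sponsor and from the Institution's IRB for the subject to enter or to remain in the trial". Minor deviations go on a comment page, with no approval step stated. Dosing errors are placed in neither class.
- **After leaving or stopping.** Section 9.2.2 lists vital signs, adverse events and medication, a telephone call and a discretionary *H. pylori* test. It lists no bismuth sample. Section 9.2.1 attaches the Day 11 sample to subjects who completed the 10 days. Section 4.6 takes out of the study those who withdraw voluntarily and stop Pylera early.
- **Analysis set.** Section 11.7.1.2 requires both blood samples for the Per Protocol population and counts leaving the study early among the major deviations. Section 11.7.1.1 defines no intent-to-treat population.

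**The concern.** The deviation and withdrawal rules read as if taken from a trial that supplies and controls its drug. Here Section 8 says no study medication is distributed, and patients take what was prescribed. Irregular intake is therefore part of the exposure the study exists to describe, yet the rules treat it as a departure that may end participation.

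The study has one scheduled post-treatment bismuth measurement per subject. If a subject is removed before it, nothing is known about bismuth under that person's pattern of use. If the subject is removed after it, the measurement may fall outside the Per Protocol set. In both cases the loss is linked to the exposure under study, so the reported distribution could describe regular users better than real-life users.

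**Working it through.** The plan has no figure to reproduce. Section 11.1 says the 200 subjects were requested and not calculated, and no misuse or dropout rate is given. The check is therefore a reading of the sections against each other, followed by an illustration on assumed rates.

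**1. Can a dosing departure lead to removal?** Yes, at someone's discretion. Section 4.6 does not limit non-compliance to study procedures, and criterion 4 is open to both investigator and sponsor. Section 11.6 names incorrect dosage as a deviation. If it is rated major, two approvals are needed for the subject to stay.

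**2. When would it be noticed?**
- Section 9.2 schedules no contact between Day 0 and Day 11; events are recorded only if the patient contacts the site.
- Section 9.2.1 records compliance at the Day 11 visit, where the sample is also taken. The sampling form in Section 11.5.1 records intake times at the draw.
- Loss before sampling therefore mainly concerns subjects who contact the site mid-course or stop early. For the former, Section 10.4.3.3 has misuse, overdose and dosing errors reported to the sponsor within 24 hours, and the sponsor may act under criterion 4.
- Section 11.6 also provides for retrospective appraisal of a major deviation that had not been reported, so a subject's status can be reopened after the sample exists.

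**3. What is lost?** A subject withdrawn before Day 11, or stopping early, has no listed post-treatment bismuth sample and cannot meet the two-sample condition. Early withdrawal is itself a listed reason for falling outside the Per Protocol set.

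**4. In which direction?** Extra capsules or a longer course would be expected to raise bismuth, and missed capsules or a shorter course to lower it. Losing over-users shifts the retained distribution down; losing under-users shifts it up. The documents do not say which group is larger.

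**5. Illustration of precision.** Assume a share s of 200 subjects departs from prescribed intake, so m = 200 × s, and that n of these are sampled.

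- One-sided 95% upper bound when none exceeds 50 µg/L: 1 − 0.05^(1/n)
- Chance of seeing at least one exceedance if 10% of this group truly exceed: 1 − 0.9^n

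| Assumed s | m | Assumed loss | n | Upper bound, none seen | Chance of seeing at least one |
|---|---|---|---|---|---|
| 5% | 10 | none | 10 | 25.9% | 65.1% |
| 5% | 10 | 10% | 9 | 28.3% | 61.3% |
| 5% | 10 | half | 5 | 45.1% | 41.0% |
| 10% | 20 | none | 20 | 13.9% | 87.8% |
| 10% | 20 | 10% | 18 | 15.3% | 85.0% |
| 10% | 20 | half | 10 | 25.9% | 65.1% |
| 20% | 40 | none | 40 | 7.2% | 98.5% |
| 20% | 40 | 10% | 36 | 8.0% | 97.7% |
| 20% | 40 | half | 20 | 13.9% | 87.8% |

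For example, with n = 20: 1 − 0.05^(1/20) = 0.139. A 10% loss moves the bound little; losing half nearly doubles it.

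**The case against.** The strongest reply is that the protocol already treats misuse as something to record. Section 7 requires compliance to be documented, Section 10.4.3.3 makes misuse and dosing errors reportable without calling for withdrawal, and Section 7.7 has non-adherent subjects assessed, not removed. Withdrawal under Section 4.6 is discretionary. The examples under criterion 8 are missed visits and evaluations, and the adherence item in Section 11.6 concerns study procedures. Most dosing departures would surface only at the visit where blood is drawn.

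Much of this stands, and it rules out three stronger readings that a reader might infer:

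- **That every wrongly dosing subject needs sponsor and IRB approval to stay.** The requirement covers major deviations only, and neither Section 11.6 nor Section 11.7.1.2 names dosing errors as major.
- **That misusers as a group are lost before Day 11.** The visit schedule makes this unlikely for most of them.
- **That the loss favours a finding of no accumulation.** This would hold only if over-users predominate among those lost, which nothing in the documents shows.

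The reply does not settle the conflict itself. Recording misuse does not prevent removal for it, and discretion to remove subjects because of the exposure under study is a route to selection. Leaving dosing errors unclassified means the answer may differ from case to case.

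**Conclusion.** The conflict between Section 1.2 and Sections 4.6 and 11.6 is real, and the text permits loss of some subjects whom the study was requested to observe. It does not require that loss. The subjects exposed to it are those who contact the site mid-course, those who stop early, and those whose deviation is rated major on later appraisal.

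The size is unknown. The bounds above are arithmetically exact but rest on assumed misuse shares of 5% to 20% and assumed losses of none to half; with the visit schedule as written, half is probably high. The direction of bias is undetermined. The point merits correction because the wording touches the study's stated purpose and is cheap to change, not because a large distortion has been shown.

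**What to change.** Reconcile the sections by amendment:

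- **Section 11.6:** state that departures from the prescribed Pylera or PPI intake (missed, extra or mistimed doses, shorter or longer course) are recorded as study observations. They are not in themselves grounds for removal from the study or from its bismuth data, and need no approval for the subject to remain.
- **Section 4.6:** limit non-compliance and criterion 4 to study procedures, consent or eligibility problems.
- **Sections 4.6, 9.2.2 and the flowchart:** keep the Day 11 bismuth sample for these subjects, including early stoppers, unless they withdraw consent.
- **Section 11.7.1.2:** make the list of major deviations agree with these statements.

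Decisions about a subject's care and treatment are unaffected; the change concerns participation, sampling and analysis only.

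The cost is amendment wording, a few additional Day 11 draws and a more heterogeneous sample, which is what Section 1.2 asks for. One limit should be acknowledged: a Day 11 sample from someone who stopped much earlier says little about levels during treatment. With the elimination constant of 0.0347 per hour in Section 11.7.7, and a stop assumed 144 hours before the draw, e^(−0.0347 × 144) = 0.007 of the level remains. Such results should be read with the time since last intake, which the form in Section 11.5.1 already captures.

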11.7 DATA ANALYSIS

A detailed Statistical Analysis Plan (SAP) will be developed and filed before database lock.

Data from this study will be analyzed in a descriptive fashion. Summary tables will be produced at the interim analysis stage and after all 200 subjects have completed the study and following database lock.

11.7.1 Samples for analysis

11.7.1.1 Intent-to-treat Population

Not applicable.

11.7.1.2 Per Protocol Population

The Per Protocol (PP) population will consist of all subjects who have met the following criteria:

- have provided 1st and 2nd blood samples for plasma and whole blood PK data;
- have completed the study without any major protocol violations or other events considered to have potential impact to the full PK profile.

Major protocol deviations include all significant deviations to the protocol related to the inclusion/exclusion criteria, to the conduct of the trial, to the subject management or assessment of safety data and may include but not limited to the following:

- conduct of any study procedure prior to the signature of the ICF
- major deviation to study procedures
- premature withdrawal from study

11.7.1.3 Safety Population

The Safety Population will be defined as all enrolled subjects who have provided informed consent.

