7 ADMINISTRATIVE PROCEDURES AND ETHICAL CONSIDERATIONS

Aptalis Pharma US, Inc. ensures the following obligations and administrative aspects of the study have been discussed with Investigators. These are described below:

- The Investigator must acknowledge Aptalis Pharma US, Inc. has instituted a Quality Assurance program according to Good Clinical Practices (GCPs), International Conference on Harmonisation (ICH) Guidelines and applicable laws and regulations;
- The Investigator must agree to allow study monitoring activities throughout the conduct of the study;
- The Investigator must agree to the inspection of study-related records by regulatory agency and/or Aptalis Pharma US, Inc. or designate;
- The Investigator must adhere to the European Medicines Agency (EMA) principles in addition to any applicable or local requirements.
- The Investigator must document in the CRF, Pylera® treatment description and compliance: date of first dose, date and hour of last dose, premature discontinuation of Pylera®, and if the subject took all doses.

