8 MATERIALS AND STUDY DRUG

Not applicable.

This study is designed to capture pharmacokinetics information on bismuth and TMB in a naturalistic real-world setting. No study medication *per se* will be distributed during the course of this study. The patient will be instructed to take the Pylera® as prescribed by the Investigator.

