9.1 INCLUSION PROCEDURES

9.1.1 Informed Consent / Instructions to subjects

Before a subject is enrolled in this study and prior to the performance of any evaluations or study procedures, the Investigator or designee must explain the study to the subject in sufficient detail to allow for her/his informed decision to participate. The Investigator must adopt a standardized approach for obtaining Informed Consent from each subject. Availability of alternative treatment must be fully explained to the subject and documented in the Informed Consent Form (ICF). If the subject understands the requirements of the study and agrees to participate, the subject will sign the ICF. This form must also be signed by the Investigator or designee. All signatures must be dated. If the Investigator chooses to alter a medical regimen of the subject for the purpose of enrolling the subject in this study, the Informed Consent for the study should be signed at that time and prior to any alteration in the subject's ongoing therapeutic regimen. A copy of the signed and dated consent form must be given to the subject before the subject initiates the study. The signed ICF must be available for an Aptalis Pharma US, Inc. CRA or designee for on-site review. Upon willingness to participate in the study, each subject will be enrolled in the study by assignment of a unique sequential enrollment number for each study site.

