9.1.2 Observations and Measurements

Following the granting of Informed Consent, each subject will be assigned a subject number in sequential order.

The following Inclusion Visit procedures and evaluations in addition to procedures normally conducted as part of standard of care will be performed after Informed Consent will be recorded in the appropriate sections of the CRF:

- Demographic data
- Confirmation of inclusion and exclusion criteria
- Date of Pylera® prescription
- Name of prescribed PPI
- Vital signs measurement (blood pressure, pulse rate), height and weight
- Disease history regarding *H. pylori* infection with previous *H. pylori* treatment and diagnostic tests with date and results (negative/positive)
- Co-morbidities, medical/surgical history
- Recording of prior and concomitant medications

Subjects will provide one blood sample as the baseline sample (D0 sample) for assessment of plasma and whole blood bismuth concentrations and whole blood trimethylbismuth (TMB) concentrations as per the procedures outlined in Appendix 2.

Once the D0 sampling is complete, subjects will be given an appointment for the second blood sampling (D11 sample) and subjects may initiate treatment with Pylera®.

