11.7.4.2 Secondary Efficacy Endpoints

The eradication rate of Pylera®, defined as the proportion of negative test of diagnostic *H. pylori* test (breath test, biopsy, or other test at the discretion of the Investigator) conducted at least 28 days following the end of treatment with Pylera®, will be calculated, including a 95% confidence interval. The eradication rates will be calculated for both the Safety and Per Protocol Populations.

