11.7.6 Safety Analysis

Safety evaluations include vital signs, AEs and concomitant medications.

The safety profile will be assessed in terms of overall AEs, vital signs findings, and concomitant medication usage over the 10-day treatment period, as well as at the 4 weeks follow-up period after treatment.

Vital signs will be summarized descriptively. Change from baseline will also be summarized.

Prior and concomitant medications will be coded using the World Health Organization (WHO) Drug dictionary. Medications initiated prior to start of study medication and maintained during

the study, or taken during the course of the trial will be considered as concomitant medications. Concomitant medications will be summarized according to the preferred terms.

Adverse events will be coded using the Medical Dictionary for Regulatory Activities (MedDRA). The number and percentage of subjects who experienced any AE as well as serious AE will be presented by system organ class and by preferred term within system organ class. All AEs will be similarly presented by seriousness criteria and by relationship to Pylera® (related/not related).

Safety analysis will be performed on the safety population for all subjects and for treatment successes and failures separately. No statistical comparisons will be performed.

There will be an additional follow-up for neurological adverse events indicative of encephalopathy through a separate and concomitant safety program, i.e. the Intensive Monitoring Program, as part of Risk management plan of Pylera®. A “Pharmacovigilance reporting form – for neurological events with bismuth” shall be completed for each case where neurological symptoms listed in the Appendix 3, accompanied or not by bismuth whole blood concentration above 50 µg/L occur. There will be a case review and confirmation by the Scientific Committee of the Intensive Monitoring Program for the diagnosis of encephalopathy. The assessment of the correlation between bismuth concentration and occurrence of neurological symptoms will be provided in the Periodic Safety Update Reports (PSUR) and in the reports from the Intensive Monitoring Program.

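### The Safety Population is defined by consent and not by dosing, so adverse event percentages can include never-exposed subjects and pre-dose events

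*Protocol*

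**What the plan says.** - **Definition.** Protocol Section 11.7.1.3 takes as the Safety Population "all enrolled subjects who have provided informed consent". Nothing in the definition refers to taking the drug.
- **Enrolment.** Section 9.1.1 ties enrolment to willingness to participate: "each subject will be enrolled in the study by assignment of a unique sequential enrollment number for each study site".
- **Start of dosing.** Under Section 9.1.2 the Day 0 blood sample comes next, and only then "subjects may initiate treatment with Pylera". Section 8 says the study distributes no medication: "The patient will be instructed to take the Pylera® as prescribed by the Investigator".
- **Use for safety.** Section 11.7.6: "Safety analysis will be performed on the safety population for all subjects and for treatment successes and failures separately". Adverse events and serious adverse events are given as numbers and percentages of subjects.
- **Event window.** Section 10 records adverse events from signature of consent, not from first dose.
- **Use for eradication.** Section 11.7.4.2: "The eradication rates will be calculated for both the Safety and Per Protocol Populations".
- **Other sets.** The intent-to-treat population is marked not applicable (Section 11.7.1.1). The Per Protocol set requires both blood samples and no major violation (Section 11.7.1.2). No set is defined by exposure alone.
- **Exposure data.** Section 7 requires the CRF to hold "date of first dose, date and hour of last dose, premature discontinuation of Pylera®, and if the subject took all doses".

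**The concern.** A percentage meant to describe how often people taking a drug have adverse events should be taken over people who took it. Here a subject enters the denominator by consenting. The study observes ordinary prescriptions in real-life use, and Section 1.2 names poor compliance among the things to be observed, so some consenting subjects may never start.

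Such subjects cannot have a drug-related event, and they pull that percentage down. In a post-marketing safety study, a lower percentage favours the product. The numerator is not tied to exposure either: an event between consent and first dose can be counted in the same table as events on treatment. Section 11.7.6, however, frames the assessment around the 10-day treatment period and the four weeks after it, and neither period exists for a subject who was never dosed.

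**Working it through.** The protocol gives no derived figure to reproduce on this point. The 200 subjects were requested by the authorities, without a calculation (Section 11.1).

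**1. Can a never-dosed subject be in the set?** Two routes exist.
- A subject may withdraw after consent but before receiving the prescription. Section 4.6 calls this a screening failure and replaces the subject, but no section removes the subject from the Safety Population.
- A subject may hold the prescription, consent, give the Day 0 sample and then take no capsule. Nothing removes this subject either.

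**2. Effect on an adverse event percentage.** Let f be the fraction of the Safety Population that took at least one dose, p1 the percentage with an event among dosed subjects, and p0 the percentage among never-dosed subjects (events after consent).

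Reported percentage = f × p1 + (1 − f) × p0

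For drug-related events p0 = 0, so the reported figure is f × p1. Assumptions, since the protocol gives neither figure: p1 = 30%, and 3% to 10% never dosed.
- f = 0.97: 0.97 × 30% = 29.1%
- f = 0.90: 0.90 × 30% = 27.0%

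For events of any cause p0 may exceed zero, and pre-dose events in dosed subjects raise p1. Both work against the dilution.

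**3. The same with a rate from the protocol.** Section 1.1 reports headache in 7/32 = 22% of subjects in the earlier pharmacokinetic study. Applied to 200 dosed subjects this is about 44. With k never-dosed subjects (k assumed) and no headache among them:

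| k | Share never dosed | Reported headache rate |
|---|---|---|
| 0 | 0% | 44/200 = 22.0% |
| 10 | 10/210 = 4.8% | 44/210 = 21.0% |
| 20 | 20/220 = 9.1% | 44/220 = 20.0% |

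**4. Eradication.** Section 11.7.4.2 defines the rate as the proportion of negative tests among tests done at least 28 days after the end of treatment. A never-dosed subject has no end of treatment, hence no qualifying test. Take the 93.3% of the European Phase III trial (Section 1.1), about 187 of 200 dosed subjects, with 95% Wilson intervals.
- Only qualifying tests counted: 187/200 = 93.5% (89.2 to 96.2) for every k.
- All Safety subjects counted, untested taken as not eradicated: k = 10 gives 187/210 = 89.0% (84.1 to 92.6); k = 20 gives 187/220 = 85.0% (79.7 to 89.1).

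The second line needs a rule that the protocol does not state. The observed-case rule of Section 11.7.1.4 covers safety variables only, so it does not settle the matter.

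**The case against.** **The undosed group should be small.** Inclusion criterion 1 requires a prescription already received, and Section 3.2 considers inclusion only after the decision to treat. One could also read screening failures as never enrolled. This limits the size. It does not remove the point, because Section 9.1.1 enrols on willingness to participate and a subject with a prescription who takes no capsule still counts.

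**No decision rests on these percentages.** The analysis is descriptive, Section 11.7.6 plans no statistical comparisons, and the primary question rests on measured bismuth concentrations, which this denominator does not dilute. That stands, and it keeps the point modest.

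**A set based on consent matches the recording window.** It also captures events around the Day 0 blood draw. This is a fair reason to report such events, but not to mix them with events after exposure. It also means that a reader cannot infer a sure downward bias in the all-cause percentages, since pre-dose events can add to the numerator.

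**Eradication.** A reader might infer that the Safety-population rate must fall, for example from 93.3% to 90.5% (× 0.97) or 84.0% (× 0.90). The text does not support this: the rate is a proportion of tests, and the fall requires counting untested subjects as not eradicated.

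**Successes and failures.** A reader might also blame this definition if the two safety subgroups do not add up to the total. Dosed subjects without a test fit neither group either, and after early discontinuation the test is at the investigator's discretion (Section 9.2.2). The gap would remain after the definition is corrected.

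**Conclusion.** The point holds for the safety tables. The protocol states a rule, rather than leaving a detail open, under which adverse event percentages can include unexposed subjects in the denominator and pre-dose events in the numerator. Under the assumed 3% to 10% never dosed, an assumed 30% rate loses 0.9 to 3.0 percentage points if never-dosed subjects have no events. The loss may be smaller, and for all-cause events the direction is not certain. For eradication the documents support only a conditional statement: the rate is affected if untested Safety subjects are put in the denominator, and is otherwise unchanged. The primary bismuth analysis is not touched. The correction is worth making because it costs almost nothing and gives safety percentages their ordinary meaning.

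**What to change.** 1. In Section 11.7.1.3, define the Safety Population as enrolled, consented subjects who took at least one dose of Pylera®, identified by the first-dose date in the CRF. Add a sentence on subjects whose first-dose date is unknown, for instance those lost before the end-of-treatment visit, where Section 9.2.1 records treatment.
2. List events between consent and first dose separately, so that nothing around the Day 0 sample is lost.
3. Report consented but undosed subjects in the disposition table.
4. Use the dosed set as the broader population in Section 11.7.4.2, and say whether dosed subjects without a qualifying test are in the eradication denominator.

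Cost: one changed definition, one short listing and one clarifying sentence on the denominator. No new data are needed.
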